## Secondary Objective 4: Hypotheses 4a & 4b

Hypothesis 4 seeks to determine whether there is a moderating effect of EDA and negative behavior variables on the impact of the environment. It is anticipated that there is greater benefit of the SADE intervention for ASD children with greater ASD severity, decreased IQ, increased sensory over-responsivity, higher dental anxiety, and/or younger age. These models are exploratory and will be assessed initial with each moderator alone. Then a stepwise regression model will be built to see if there are moderators that are more important than others. The previously described associations will assist us in determining if there is a risk of collinearity amongst the variables.

Hyp 4: EDA or Negative behavior =  $B_0$  +  $B_1$ \*Environment + B2\*Moderators + B3\*(Environment\*Moderators) + Covariates

## Secondary Objective 5: Hypotheses 5a & 5b

Hypotheses 5a and 5b are similar, examining the environment difference on the costs and quality of care. The general model is presented below. Quality of care will be determined by scoring of pre- vs. post- intra-oral photographs on the OHI-S and Plaque Index measures. Health care costs are defined as personnel time burden, including direct costs of the intervention (e.g., training, materials, overhead, and direct patient care). The cost-effectiveness of the SADE intervention will be represented in the form of an incremental cost-effectiveness ratio of the cost (C) relative to the quality of care (E):  $(C_{SADE} - C_{RDE})/(E_{SADE} - E_{RDE})$ .

Hyp 5: Cost or Quality = 
$$B_0 + B_1*Environment$$

These models are paired and will involve paired t-tests or non-parametric corollary for continuous outcomes if the outcome is normal or non-normally distributed, respectively. For dichotomous outcomes (e.g., need for sedation), McNemar's test will be used to examined differences in need for the paired observations.

Cost Effectiveness Analysis. In assessment of medical interventions, cost-effectiveness evaluations become increasingly relevant. Using this evaluation approach and the comparative intervention RDE as the reference standard, the cost-effectiveness of the SADE intervention will be represented in the form of an incremental cost-effectiveness ratio as:  $(C_1 - C_0)/(E_1 - E_0)$ , where the subscript 1 refers to the SADE intervention arm and the subscript 0 refers to the RDE comparative arm.  $C_1$  represents the average net cost of implementing the intervention;  $C_0$  represents the average net cost of the RDE comparative arm;  $E_1$  represents the quality of care associated with the SADE intervention; and  $E_0$  represents the quality of care associated with RDE. We will consider alternative effectiveness outcomes.

We will use alternative measures of effectiveness in conducting our economic evaluation of the intervention. We will also combine several of the effectiveness scales into a measure of dental performance using structural equations models with unobservable dental health status as a latent variable in a multiple indicators, multiple causes framework. In this approach, all structural measures of dental treatment including patient functional status and patient outcome measures will be used as health status indicators, whereas clinical, environmental, and background characteristics will serve as causal factors in explaining dental health status changes. We will compute confidence intervals for the cost-effectiveness ratios using bootstrapping and develop cost-effectiveness acceptance curves. In this approach, all structural measures of dental treatment including patient functional status and patient outcome measures will be used as health status indicators, whereas clinical, environmental, and background characteristics will serve as causal factors in explaining dental health status changes.

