Note-3: (COVID-19 modifications) At the beginning of the COVID-19 pandemic (March 2020), all research activities were discontinued. At that time, all participants had been recruited and completed Visits 1-3. Twenty-five participants had not completed the final visit (second dental cleaning). Once permission to resume research activities is provided by USC and CHLA we will adhere to all COVID-19-related guidelines and regulations from CHLA and USC. To protect the health and safety of patients and staff during the COVID-19 pandemic, CHLA now requires participants take a COVID-19 test 72 hours prior to a scheduled dental cleaning visit. This will require an extra visit for our participants. Thus, for the remaining 25 participants who will be completing their second dental visit, the study team will inform the parent/legal guardian of the COVID-19 test (until it is no longer a requirement at CHLA) and the rideshare option for both the COVID-19 testing and the dental cleaning visit. The study team will follow the most current CHLA procedures and guidelines and as changes are made, we will abide by the most current CHLA procedures and guidelines.

 Record unanticipated problems as reported by subject/parent or observed by investigator/dental staff (See CRF 27: Unanticipated Problem Form).

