# 12.4 Final Analysis Plan

Descriptive statistics will be performed for all variables of interest to describe the participant population at baseline, including attrition rate and missing data, to compare those randomized to SADE first vs. those randomized to RDE first. We anticipate a low attrition rate (~10%) and will impute missing data for intent-to-treat analyses using Markov Chain Monte Carlo (MCMC)

imputation with multiple values imputer for each missing value averaged for an estimation for analyses. Bivariate associations between outcomes (physiological anxiety and children's negative behavioral responses), environment (SADE or RDE), and covariates (age, gender, order of visit, autism severity, IQ, and sensory sensitivity) will be described. The primary objective of determining difference between dental environments will be tested using intent-to-treat models examining the within-subject factor of dental environment (SADE vs RDE) using repeated measures ANCOVA for each outcome. *A priori* covariates include age (continuous), randomized order of visit, gender, and temperature. Other participant characteristics that are unbalanced between order of visits will be included as covariates *ad hoc*.

The secondary objective of examining the mediating effect of physiologic response on behavioral outcomes will be tested by first examining the bivariate relationships between EDA and behavioral outcomes, and then adding EDA estimates (SCL and NS-SCR) to models of dental environment difference on behavioral outcomes, and examining the change in the within group coefficients. A change in coefficient >15% will be considered evidence of mediation. While we have several outcomes, we specify only one mediator, thus we will apply a rational approach to examination of multiple outcomes, and will assess the fidelity of our study by estimating effect sizes (Cohen's d) of the dental environment before and after the mediation factors are assessed to confirm that statistical results were supported by clinical relevance of findings. If physiological anxiety does mediate the environment's effect on negative behavioral responses, we anticipate that the anticipated effect of environment will be eliminated once we add in EDA to the models specified in Hypothesis 2. Analyses will be performed using SPSS (v.22); a priori two-sided  $\square = 0.05$ .

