# **Primary Objective: Hypothesis 1**

The primary objective is to test the effect of the environment (SADE vs RDE) on physiological anxiety. Hypothesis 1 specifies an effect of environment on the outcome, thus the main effect of interest will be  $B_1$ , the dental environment.

Hyp 1: EDA =  $B_0$  +  $B_1$ \*Environment + Covariates

## Secondary Objective 2: Hypothesis 2

The secondary objective explores further outcomes and mechanisms of the group differences. Hypothesis 2 is analogous to those in the primary aim and have the same coefficients of interest. However, there are multiple, secondary outcomes including behavioral distress, perception of pain, and sensory discomfort). As noted above, we will apply a rational approach to examination of multiple outcomes and will assess effect sizes of the coefficients, in addition to the statistical significance.

Hyp 2: Negative behavior =  $B_0 + B_1$ \*Environment + Covariates

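### The Hypothesis 5 cost and quality tests leave out visit period, so continuous outcomes lose power if second visits differ from first visits

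*Combined protocol and SAP*

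**What the plan says.** In Section 12.4, Secondary Objective 5, the formula labelled "Hyp 5: Cost or Quality" has an intercept and an environment term and nothing else. The tests follow from it: "These models are paired and will involve paired t-tests or non-parametric corollary for continuous outcomes", and for yes/no outcomes such as need for sedation, "McNemar's test will be used to examined differences in need for the paired observations".

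The formulas for Hypotheses 1 to 4 all end in a covariate term; Hypothesis 1, for instance, ends in "Environment + Covariates". The general text of Section 12.4 tests the environment effect "using repeated measures ANCOVA for each outcome" and states that the a priori "covariates include age (continuous), randomized order of visit, gender, and temperature". Section 5.4.1 shows that order is the randomised factor, blocked within gender-age strata.

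The cost-effectiveness paragraphs that close Section 12.4 add a latent-variable model and bootstrap intervals. They name neither order nor period, so nothing later puts it back for this objective.

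**The concern.** Each child's comparison of the two environments is also a comparison of a second visit with a first. If second visits run differently whatever the environment, that shift has one sign in children who had SADE second and the other sign in children who had it first. A paired test does not separate the two orders. It treats the shift as scatter between children, so the standard error is too large.

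A period effect is plausible from the documents. Section 6.1 aims for the same dentist and assistant at both cleanings, so the second visit is more familiar; this could affect duration and hands needed for restraint. Section 7.3 (Visit 4, Note-3) leaves 25 second visits, and no first visits, to be done under pandemic procedures, where "CHLA now requires participants take a COVID-19 test 72 hours prior to a scheduled dental cleaning visit".

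At stake is the precision of the tests on duration, staffing and cleaning quality, and of the bootstrap interval for the cost-effectiveness ratio. The information needed to recover it is already recorded for every child.

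**Working it through.** **Inputs.** From Section 12.2: 165 children with both visits, d = 0.22, 80% power. From Section 12.4: two-sided alpha 0.05. Assumed, because the documents give no value: 1:1 allocation to order, and a period effect π (second visit minus first) of 0.3, 0.5 or 0.8 SD of the within-child difference. The documents give no effect size for cost or quality, so d = 0.22 is borrowed.

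**The plan's own figure.** n = ((1.960 + 0.842)/0.22)² = 162.2, so 163 by the normal formula and 165 by the noncentral t; power at 165 is 0.802. The figure therefore reproduces at two-sided 0.05. Section 12.2 also mentions 0.025. Taken as two-sided, that needs 199 children and gives power 0.713 at 165, so it is not the basis of the 165. I use two-sided 0.05.

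**Model.** Take the SADE minus RDE difference, with SD 1 within each order. Its mean is δ + π in the n1 children with SADE second and δ − π in the n2 with SADE first; N = n1 + n2.

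- Paired t: the estimate is centred on δ + π(n1 − n2)/N, and the SD it uses is s = √(1 + π²·4n1n2/N²).
- Period-adjusted: the estimate is the average of the two order means, centred on δ, with standard error ½√(1/n1 + 1/n2).

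**Balanced orders.** The standard error is inflated by √(1 + π²) = 1.04, 1.12 and 1.28. The critical value is 1.975 and 0.22·√165 = 2.826, so power ≈ Φ(2.826 − 1.975·s):

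- π = 0.3: Φ(2.826 − 1.975 × 1.044) = Φ(0.76) = 0.78
- π = 0.5: Φ(2.826 − 1.975 × 1.118) = Φ(0.62) = 0.73
- π = 0.8: Φ(2.826 − 1.975 × 1.281) = Φ(0.30) = 0.62

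An odd total of 165 cannot split exactly. At 83/82 the extra child moves the mean by π/165 one way or the other. Power is then 0.79, 0.74 and 0.64 if that helps, and 0.77, 0.72 and 0.59 if it hurts; simulation agrees. The period-adjusted test stays at 0.80. Type I error of the paired t, 2Φ(−1.975·s), is about 0.04, 0.03 and 0.01.

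**Unequal completers.** Results at π = 0.3, 0.5 and 0.8:

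| Completers by order | Shift in estimate (SD) | Paired-t type I error |
|---|---|---|
| 83/82 | 0.002, 0.003, 0.005 | 0.04, 0.03, 0.01 |
| 89/76 | 0.024, 0.039, 0.063 | about 0.05, 0.05, 0.04 |
| 95/70 | 0.045, 0.076, 0.121 | 0.08, 0.11, 0.17 |

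The period-adjusted test holds about 0.05 in every row. If 110 children per order are randomised and 165 complete for reasons unrelated to order, the number completing in one order has SD √(165 × ¼ × 55/219) = 3.2. Then 95% of splits lie between 76/89 and 89/76, and a split as extreme as 95/70 has probability about 0.0002.

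**Binary outcomes (simulated over assumed period effects).** With balanced orders McNemar's type I error is 0.037 to 0.052, and at a period log-odds of −0.8 power is 0.64 with or without adjustment. At 95/70 its type I error is 0.062 to 0.097, against 0.051 to 0.053 for Mainland-Gart.

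**The case against.** The strongest defence is that the design does most of the work. Order is blocked, so the two orders should be close to equal among those randomised, and a period effect then nearly cancels from the mean difference. The paired t remains valid, merely conservative; McNemar's test is close to nominal; and the point estimate of the cost-effectiveness ratio hardly moves. These are secondary outcomes in a Phase II trial, and at π = 0.3 the loss is only about one to three points of power. All of this stands.

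A reader might go further and infer that the Hypothesis 5 results will be biased, or that McNemar's test will mislead. The documents do not support that. It needs a period effect together with dropout clearly related to order, and nothing in them shows such dropout. It cannot be ruled out either: under Section 7.5, children without a second cleaning within eight months are treated as withdrawn, and that loss comes after one environment has been experienced.

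The grounds for a period effect are also mixed. Plaque is a weak argument: quality compares scores before and after each cleaning, Visit 3 requires at least four months since the last cleaning (Section 5.1), and Section 8.1 places it near the usual recall, so both visits follow a cleaning by a broadly similar interval. Every child has had a prior cleaning, so familiarity is only partly new. A single period term absorbs only the average of whatever the 25 pandemic-era visits add.

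It could also be said that the general ANCOVA text, which speaks of each outcome, already covers cost and quality. But that sentence concerns the primary objective, and the Objective 5 text names its own tests.

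**Conclusion.** The omission is real, and for continuous outcomes it costs power. Under the assumptions above, 0.80 falls to about 0.77–0.79, 0.72–0.74 or 0.59–0.64 for period effects of 0.3, 0.5 and 0.8 SD, with type I error below nominal. The size rests on a borrowed d, on assumed period effects and on near-balanced orders; with no period effect nothing is lost. Type I error above nominal is a conditional risk, to be judged from the actual count of completers in each order. For binary outcomes the case for adjustment is protection against unequal completers, not power. This is a minor but nearly free improvement, not a threat to the trial's conclusions.

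**What to change.** In Section 12.4, Secondary Objective 5:

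- **Continuous outcomes:** fit environment plus period, that is, compare the within-child SADE minus RDE differences between the two orders. Name visit period explicitly: a between-child main effect of order alone does not remove a visit difference from the within-child contrast.
- **Non-normal outcomes:** use a rank-sum test of the within-child differences by order.
- **Binary outcomes:** use Mainland-Gart or its exact version.
- **Cost-effectiveness ratio:** resample children within order when bootstrapping.
- Report the number of completers in each order.

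The cost is SAP wording and one degree of freedom; no new data are needed. The one real drawback is for rare outcomes such as sedation, where few discordant pairs leave little information once they are split by order. Section 16.4 places the final export after database lock, and Section 7.3 describes 25 second visits as still outstanding, so on the document's own timetable the change can be prespecified.

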Cost-Savings (Researcher- scored)	Number of hands required for restraint, calculated from video-recordings and notes.	Observational (1)	Immediately following both dental cleanings.	2d	Cost- Effectiveness & Cost-Savings Form (21)
Cost-Savings (Researcher- scored, in consultation with dentist)	Need for protective stabilization, sedation, and/or anesthesia to complete cleaning.	Observational (1)	Immediately following both dental cleanings.	2d	Cost- Effectiveness & Cost-Savings Form (21)
Quality of Care (Dentist-scored)	Analysis of oral health and plaque before cleaning versus after cleaning using intra-oral photographs 90 (Rechmann et al., 2014) utilizing the Oral Health Index-Simplified  and Plaque Index. 	Observational, completion of OHI-S (12) and Plaque Index (6) based on intra-oral photographs.	Intra-oral photographs taken before and after dental cleaning; scoring to be completed at a later time.	2d	Quality of Care Recording Form (16)

Table 3. Child-descriptor variables

Child- descriptor (Completed by)	Child-descriptor & Description	Type of form (No. of Items)	When Administered	Specific Objective Tested	CRF Name (#)
ASD Diagnosis (Psychologist)	The Autism Diagnostic Observation Schedule-2 (ADOS-2) is used to confirm a diagnosis of ASD and provides a measure of autism severity.	Observational (varies)	Visit 2	2c	Autism Diagnostic Observation Schedule-2
IQ (Psychologist)	Wechsler Abbreviated Scale of Intelligence – Second Edition provides a measure of IQ	Observational (varies)	Visit 2	2c	Wechsler Abbreviated Scale of Intelligence – Second Edition
Short Sensory Profile-2 (Parent)	Sensory Sensitivity	Parent questionnaire (34)	Visit 1	2c	Sensory: Short Sensory Profile-2 (7)
Dental Anxiety (parent)	Children's Fear Survey Schedule- Dental Subscale measures dental anxiety.	Parent questionnaire (15)	Visit 1	2c	Children's Fear Survey Schedule- Dental Subscale (8)
General Anxiety (parent)	Child and Adolescent Symptom Inventory-4, Anxiety Scale	Parent questionnaire (21)	Visit 1	2c	Child and Adolescent Symptom Inventory-4, Anxiety Scale (6)
Expressive Communication Ability	Vineland Adaptive Behavior Scales-II, Expressive Communication Domain	Parent questionnaire (varies)	Visit 1	2c	Vineland Adaptive Behavior Scales- II, Expressive Communication Domain
Age of child (parent)	Age	Parent questionnaire (1)	Visit 1	2c	Family information (5)

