# **6 STUDY INTERVENTION**

# 6.1 Study Behavioral or Social Intervention(s) Description

This study will investigate the impact of adapting the dental environment on the physiological anxiety and negative responses of children with ASD undergoing a dental cleaning. Dental cleaning in a sensory adapted environment (SADE) will be compared to usual treatment for dental cleaning in a regular dental environment (RDE).

Dental cleanings in the *control condition* (RDE) and *experimental condition* (SADE) will take place in a private room in the CHLA Dental Clinic and will each require approximately 15-45 minutes to complete, and will take place four-six months apart. Every effort will be taken to ensure that both cleanings will be performed by the same SADE-trained CHLA pediatric dentistry resident and dental assistant. The SADE environment will be set up prior to the child's entrance into the dental room by a member of the research team.

Table 3 summarizes the specific modifications that comprise the SADE intervention. Specifically, visual, auditory, and deep pressure tactile stimuli are altered in an effort to maximize relaxation. It should be noted that dentists participating in our R34 pilot study indicated that the SADE did not negatively impact their ability to perform the oral cleaning in a regular manner. This was also reported by Shapiro et al. (personal communication, February 25, 2008) who conducted a similar study with children with intellectual and developmental disabilities. This will be empirically tested in the proposed study by including a measure of quality of care. Additionally, the intervention does not require permanent renovations to the dental clinic, as the equipment is portable, requiring approximately 15 minutes to set up or to remove.

Table 3. Components of the SADE Intervention.

Visual	All direct overhead fluorescent lighting and the regular dental overhead lamp will be turned off; dark colored "black-out" removable curtains will cover the windows in the private dental room. The dentist will wear a head-mounted dental lamp directed into the patient's mouth, reducing bright lights shining into the child's eyes. Slow moving visual color effects (Snoezelen) will shine onto the ceiling in the child's visual field.			
Auditory	Auditory stimuli will include rhythmic music projected via a Phillips Portable Speaker System. Music will be either Dan Gibson's Exploring Nature with Music or similar options.			

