### 12 STATISTICAL CONSIDERATIONS

# 12.1 Study Hypotheses

**Primary Objective:** To compare children's physiological anxiety (EDA - primary outcome) during the dental cleaning in SADE vs. RDE.

**Hypothesis 1:** Children will exhibit less physiological anxiety (SCL and NS-SCR frequency) during routine dental care in the SADE condition compared to the RDE.

**Secondary Objective 2:** To compare children's negative behavioral responses (behavioral distress, perception of pain, sensory discomfort - secondary outcomes) during dental cleanings in SADE vs. RDE.

**Hypothesis 2:** Children will exhibit fewer negative behavioral responses during routine dental care in the SADE condition compared to the RDE.

**Secondary Objective 3:** To test the degree to which physiological anxiety mediates the SADE intervention's effects on children's negative behavioral responses.

**Hypothesis 3:** Physiological anxiety mediates the effect of the intervention in decreasing child negative behavioral responses.

**Secondary Objective 4:** To test the degree to which specific child characteristics moderate the SADE intervention's effects on children's physiological and negative behavioral responses during dental cleaning.

**Hypothesis 4:** The magnitude of physiological and negative behavioral response change in the SADE, relative to the RDE, will be greater in children with ASD with increased sensory over-responsivity, high dental anxiety, greater ASD severity, lower IQ, and/or younger age.

**Secondary Objective 5:** To compare the SADE intervention to the RDE on quality of care, cost-effectiveness, and potential cost savings of dental cleaning.

**Hypothesis 5a:** The SADE intervention, compared to the RDE, is cost-effective and results in decreased overall costs.

**Hypothesis 5b:** The SADE intervention, compared to the RDE, results in improved quality of care as evidenced by thoroughness of dental cleaning.

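### For non-normal costs, Hypothesis 5a falls to an unnamed non-parametric test that does not compare mean cost and could disagree in sign with the plan's own cost-effectiveness ratio

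*Combined protocol and SAP*

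**What the plan says.** Section 12.1 states Hypothesis 5a as "The SADE intervention, compared to the RDE, is cost-effective and results in decreased overall costs".

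Section 12.4, under Secondary Objective 5, gives cost and quality of care one shared model: "Hypotheses 5a and 5b are similar, examining the environment difference on the costs and quality of care". It calls these models paired and prescribes "paired t-tests or non-parametric corollary for continuous outcomes if the outcome is normal or non-normally distributed, respectively". It does not name the non-parametric test, give a criterion for normality, or say what the fallback estimates. Dichotomous outcomes, with need for sedation as the example, go to McNemar's test.

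The same section builds the ICER from mean costs. Its first cost term "represents the average net cost of implementing the intervention", and the RDE term is defined in the same way. Bootstrap confidence intervals are planned for the ratios, together with cost-effectiveness acceptance curves. No confidence interval or test is specified for the mean cost difference itself.

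On what counts as cost, section 12.4 says "Health care costs are defined as personnel time burden, including direct costs of the intervention". Section 3.2.2 (Secondary Objective (d)) lists anesthesia among the components of relative cost, and Table 2 has a separate cost-savings item, "Need for protective stabilization, sedation, and/or anesthesia to complete cleaning". Section 6.1 describes the SADE equipment as "requiring approximately 15 minutes to set up or to remove".

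**The concern.** Overall cost is a total, and a total is a mean multiplied by the number of visits. A test of 5a should therefore address the mean paired difference in cost. The signed-rank test addresses something else: whether the differences are centred on zero in rank terms. A child whose difference is very large contributes at most the top rank, however large the sum.

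This matters most when a small routine difference occurs at nearly every visit and a large one at few. The plan's cost items allow that pattern: set-up time at each SADE visit against sedation or anesthesia avoided in a few children. Avoiding restraint and pharmacological management is part of the rationale in section 2. If those events enter a per-visit cost, the fallback test gives least weight to the route by which SADE might save money. The stated test of 5a and the ICER numerator could then carry opposite signs on the same data.

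**Working it through.** **The plan's own figure.** Section 12.2 gives 165 pairs for d = 0.22 at 80% power. For a paired comparison at two-sided 0.05, n = ((1.960 + 0.842)/0.22)² = 162.2, so 163. The exact t calculation gives 165, with power 0.802. The figure reproduces. No sample-size figure is given for cost, so 165 pairs is used below. All cost inputs are assumptions.

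**One fixed example.** SADE costs about 15 units more in 157 children and about 985 less in 8 (a spread of ±5, summing to zero, is added to break ties).

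- Total difference: 157 × 15 − 8 × 985 = 2,355 − 7,880 = −5,525.
- Mean: −5,525/165 = −33.5, so SADE is cheaper. The paired t-test gives p = 0.046, and the bootstrap 95% interval for the mean is −69.7 to −3.4.
- Median: +14.5.
- Signed-rank: the 8 savers hold ranks 158 to 165, so W− = 8 × (158 + 165)/2 = 1,292. All ranks sum to 165 × 166/2 = 13,695, so W+ = 12,403. The null mean is 6,847.5 and the null SD is √(165 × 166 × 331/24) = 614.6, so z = (12,403 − 6,847.5)/614.6 = 9.04. The result is highly significant in the direction that SADE costs more.

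**When this can happen.** Suppose k savers have the largest absolute differences and everyone else costs slightly more. The mean favours SADE once the saving per saver exceeds (165 − k)/k times the routine extra: 157/8 = 19.6 times for 8 savers, 149/16 = 9.3 times for 16, and 132/33 = 4.0 times for 33. Signed-rank stays significant for SADE being dearer with up to 38 savers (23%).

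**Sensitivity.** Simulated trials used 165 pairs, a normal routine difference, events independent between the two visits, and two-sided 0.05. Costs are in dollars.

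| Routine SADE − RDE (SD) | Event rate RDE / SADE | Event cost | True mean difference | Signed-rank significant in the wrong direction |
|---|---|---|---|---|
| +10 (20) | 8% / 4% | 1,500 | 10 − 0.04 × 1,500 = −50 | 97% |
| +10 (20) | 8% / 4% | 500 | 10 − 0.04 × 500 = −10 | 96% |
| −6 (20) | 4% / 6% | 1,500 | −6 + 0.02 × 1,500 = +24 | 73% |
| +10 (40) | 8% / 4% | 1,500 | −50 | 35% |
| +5 (40) | 8% / 4% | 1,500 | 5 − 0.04 × 1,500 = −55 | 6% |
| −10 (20) | 8% / 4% | 1,500 | −10 − 0.04 × 1,500 = −70 | none |
| +10 (20) | 33% / 18% | 200 | 10 − 0.15 × 200 = −20 | 2% |

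In the first three rows the paired t-test was significant in the wrong direction in under 1% of trials. It detected the true saving in only about 22% of trials in row 1 and 10% in row 2.

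**The case against.** Several objections have force.

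- **No rank test is named.** A reader might infer that the plan commits to one. It does not: a bootstrap or permutation test of the mean is also non-parametric and would avoid the problem. But signed-rank is the ordinary counterpart of the paired t-test, and nothing in the section points elsewhere.
- **Mean-based cost results are already planned.** A reader might infer that mean cost is never analysed. It is: the ICER uses average costs, and an acceptance curve read at zero willingness to pay is the bootstrap probability that mean cost is lower under SADE. This softens the point but leaves the stated test of 5a unchanged. An interval for the ratio cannot replace that test, because a negative ratio can mean cheaper and better or dearer and worse.
- **Rare events have their own test.** McNemar's test covers how often they occur, though not what they cost. Cost is defined through personnel time and direct costs, and the documents do not say that a recorded need for sedation or anesthesia is priced into a per-visit total. If the continuous outcomes are purely time-based, the mechanism for reversal largely disappears.
- **Skewed costs are plausible, not shown.** The nearest figures are in section 2, where surveys put restraint at 18–33% of children with ASD. The last row of the table shows that events that common, at a modest cost, leave almost no reversal.
- **The normality condition is partly wording.** The sentence calls the models paired, so the outcome can be read as the paired difference. Stating this would settle it.

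**Conclusion.** The point holds in limited form. Hypothesis 5a and the ICER concern overall and average cost, while the stated rule for non-normal cost leads, on its ordinary reading, to a test that does not address a mean. That mismatch is in the text and does not depend on any cost assumption.

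Its consequence does. Wrong-direction significance ran from about 6% to 97% when rare and routine costs opposed each other, fell to 2% when events were common and cheap, and was absent when both pointed the same way. A reader might infer that 5a will be answered in the wrong direction. The documents do not support that: they give no unit costs, no rates of sedation or anesthesia, and no statement that these events enter per-visit cost.

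The scope is one fallback in one secondary objective, with a mean-based analysis beside it. It is worth correcting because two planned analyses of the same hypothesis could otherwise be reported with opposite signs and no rule for which one counts.

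**What to change.** In section 12.4, Secondary Objective 5:

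1. For any cost outcome, make the SADE minus RDE arithmetic mean paired difference the quantity tested for 5a, whatever the distribution. Report it with a bootstrap confidence interval that resamples children and keeps both visits together. The same resamples can serve the ratio intervals and acceptance curves, so the three results will agree.
2. Drop the normality switch for costs, or keep a named rank test as supportive only.
3. State which items are priced into per-visit cost, and whether sedation, anesthesia and stabilization are among them.
4. For non-cost outcomes, name the fallback test and apply any normality check to the paired differences.

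This is wording only and needs no new data, visits or sample. The drawback is imprecision. If rare expensive events dominate, the interval will be wide: in the two saving scenarios in rows 1 and 2 of the table, a mean-based test found the true saving in only about 22% and 10% of trials. Hypothesis 5a may then remain inconclusive, and the report should say so.
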